6.14. Bioanalytical and Pharmacokinetic/Pharmacodynamic Methods

N/A.

6.15. Safety Analyses

The primary safety analyses will focus on comparisons of ixekizumab versus adalimumab in the Open-Label Treatment Period (Period 2). Fisher's exact test will be used for all AEs and other categorical safety data. Continuous vital sign and laboratory values will be analyzed by an ANCOVA with treatment and baseline value in the model. Type 3 sums of squares will be used. The significance of within-treatment group changes from baseline will be evaluated by testing whether the treatment group LSMeans changes from baseline are different from zero using a t-statistic. In addition to the LSMeans and tests, the standard deviation, minimum, median, and maximum will be displayed. Unless otherwise specified, change from baseline will include only those subjects with both baseline and post-baseline measures.

For safety analyses, p-values should be interpreted with caution as the analyses are intended to be descriptive and should not be thought of as hypothesis testing, unless there is a prespecified hypothesis. P-values and CIs, if reported, provide some evidence of the strength of the finding and are only useful as a flagging mechanism.

Summaries of safety data collected during the Post-Treatment Follow-Up Period will be presented separately. The categorical safety measures will be summarized with incidence rates. The continuous safety measures will be summarized using mean changes.

6.15.1. Extent of Exposure

Duration of exposure to study drug will be summarized by treatment group using descriptive statistics; the summary will also include the total exposure in patient years, mean, and median total dose. Exposure of safety population in the Open-Label Treatment Period (Period 2) will be summarized.

The duration of exposure will be calculated as follows:

- *Duration of exposure (days) =*
Date of last visit (scheduled or unscheduled) during the treatment period –
Date of first injection for the treatment period + 1

- Total exposure in patient years will be calculated as follows:

$$\text{Total exposure in patient years} = \frac{\text{Sum of duration (days) of exposures for all patients in treatment group}}{365.25}$$

- Total dose (in mg) is calculated by the summation of dose for each active injection taken during the treatment period.
- Note that the total number of injections received will be calculated using the response to the question “Was the injection given?” on the *Study administration* electronic eCRF page.

Descriptive statistics will be provided for patient days of exposure and the frequency of patients falling into the following different exposure ranges (that is, only the exposure ranges that fall within the treatment period will be presented) will be summarized:

- >0, ≥7 days, ≥14 days, ≥30 days, ≥60 days, ≥90 days, ≥120 days, ≥183 days, ≥365 days.
- >0 to <7 days, ≥7 to <14 days, ≥14 to <30 days, ≥30 to <60 days, ≥60 to <90 days, ≥90 to <120 days, ≥120 to <183 days, ≥183 to <365 days, and ≥365 days.

6.15.2. Adverse Events

6.15.2.1. Analyses of Adverse Events

Adverse events are classified based on MedDRA. A treatment-emergent adverse event (TEAE) is defined as an event that first occurred or worsened in severity after the first dose of the study medication and on or prior to the date of the last visit within the treatment period. Both the date/time of the event and the date/time of the dose (that is, injection) are considered when determining TEAEs. The MedDRA Lowest Level Term (LLT) will be used in the treatment-emergent computation. The maximum severity for each LLT during the baseline period will be used as baseline severity (in some cases baseline period is a single time point). Events with a missing severity during the treatment period will be considered treatment emergent. The treatment period will be included as post-baseline for the analysis. If an event is pre-existing during the baseline period but it has missing severity, and the event persists during the treatment period, then it will be considered as treatment-emergent, regardless of the post-baseline level of severity. Adverse events with a particular LLT will be classified as treatment-emergent if they first start on or after the first dose date in the treatment period (ie, a patient has no pre-existing conditions with that LLT) or if the severity is greater than the pre-treatment severity for that LLT.

A follow-up emergent adverse event (FEAE) is defined as an event that first occurred or worsened in severity after the date of Week 52 (Visit 11) or the ETV. The MedDRA LLT will be used when classifying FEAEs as follow-up emergent. For AEs that are ongoing at the date of Week 52 (Visit 11) or ETV, the maximum severity recorded for each LLT on the date of Week 52 (Visit 11) or ETV will be used as the follow-up baseline severity for that LLT.

If a partial or completely missing AE start date/time or end date/time is present, the following imputation rules will be utilized in the analysis:

- For the start date:
 - If year, month, and day are missing, then use the earlier of the patient's first visit date or the consent date.
 - If either month or month and day are missing, then use January 1.
 - If only day is missing, impute the first day of the month.
 - The imputed date should not be before the minimum of the patient's first visit or consent date.
- For the start time:
 - Impute as 23:59

- For the end date:
 - If year, month, and day are missing, then use the patient's last visit date in the follow-up period.
 - If either month or month and day are missing, then use December 31.
 - If only day is missing, then use the last day of the month.
 - The imputed date will not be beyond the patient's last visit date in the follow-up period.
- For the end time:
 - Impute as 23:59.
- If there is any doubt, the event will be flagged as treatment-emergent or follow-up emergent according to the corresponding study period. If a follow-up emergent event was already counted as treatment-emergent during the prior treatment period, it will not be counted as a follow-up emergent event.

An overview table will be provided and will include the frequency and percentage of patients who experienced a TEAE, TEAE by maximum severity, a treatment-emergent adverse events of special interest (AESI), serious adverse event (SAE), death, or discontinued from the study due to an AE (including death) will be summarized by treatment group for the Open-Label Treatment Period.

In general, for all AE-related summaries, the number and percentage of patients experiencing the events will be presented by dosing regimen. When the SOC is presented, events will be ordered by decreasing frequency in the ixekizumab treatment group within SOC. When the SOC is not presented, the events will be ordered by decreasing frequency in the ixekizumab treatment group. For incidence counts, each patient will be counted only once within each PT and within each SOC. Percentages will be based on the number of patients in a particular treatment group. For events that are gender specific, the denominator and computation of the percentage will include only patients from the given gender.

The following summary tables will be provided for the Open-Label Treatment Period (Safety Population):

- An overview summary of AEs
- TEAEs, by SOC and PT
- TEAEs, by PT
- TEAEs by maximum severity, by SOC and PT

The following summary tables will be provided for the Post-Treatment Follow-Up Period (Follow-Up Population):

- FEAEs, by maximum severity, by SOC and PT

By-patient listing of all TEAEs will be provided.

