10.3.4.1. Adverse Events

AEs are classified based on the Medical Dictionary for Regulatory Activities (MedDRA). A TEAE is defined as an event that first occurred or worsened in severity after the first dose of study treatment and on or prior to the date of the last visit within the treatment period. Both the date/time of the event and the date/time of the dose (ie, injection) are considered when determining TEAEs. For each TEAE, the severity is recorded according to the patient's or physician's perceived severity of the event (mild, moderate, or severe). A follow-up emergent adverse event (FEAE) is defined as an event that first occurred or worsened in severity after the date of Week 52 (Visit 11) or the ETV. For events that are sex-specific, the denominator and computation of the percentage will only include subjects from the given sex.

An overall summary of AEs will be provided for Period 2, including the number and percentage of subjects who experienced TEAEs, TEAEs by maximum severity, death, SAEs, TEAEs related to study drug, discontinuations from treatment due to an AE, and treatment-emergent adverse events of special interest. TEAEs (all, by maximum severity, and TEAEs possibly related to study drug by the investigator), SAEs including deaths, and AEs that lead to treatment discontinuation will be summarized and analyzed by MedDRA system organ class (SOC) and preferred term.

In addition to general safety parameters, safety information on specific topics of adverse events of special interest will also be presented. Potential adverse events of special interest will be identified by a standardized MedDRA query (SMQ) or a Lilly-defined MedDRA preferred term listing.

Follow-Up emergent AEs, SAEs including deaths, and AEs that lead to study discontinuation will be summarized by MedDRA system organ class and preferred term for Period 3.

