6.1.3. Analysis Populations

The follow analysis populations will be used:

Intent to Treat Population (ITT): The ITT Population consists of all randomized patients. Even if the patient does not take the assigned treatment, does not receive the correct treatment, does not receive any medication, or otherwise does not follow the protocol, the patients will be analyzed according to the treatment to which they were assigned at Week 0. Unless otherwise specified, all efficacy and health outcomes analyses for the Open-Label Treatment Period (Period 2) will be conducted on the ITT population.

Safety Population: The Safety Population is defined as all randomized patients who received at least 1 dose of study treatment. Patients will be analyzed according to the treatment to which they were assigned at Week 0. Unless otherwise specified, all safety analyses for the Open-Label Treatment Period will be conducted on the Safety Population.

Post-Treatment Follow-Up Population: The Post-Treatment Follow-Up Population consists of all randomized patients who received at least 1 dose of study treatment during Period 2 and have entered the Post-Treatment Follow-Up Period. Safety analyses for Period 3 (Post-Treatment Follow-Up Period) will be conducted on this population. Patients will be analyzed according to the last treatment they received before entering Period 3 (see treatment groups defined in [Table RHCF.6.1](#)).

[Table RHCF.6.2](#) gives the description of each of the population sets in the study as well as their intended analysis purposes.

Table RHCF.6.2. Efficacy, Health Outcomes, and Safety Measures Summarized and/or Analyzed for Each Analysis Population

Population Name	Measurement Summarization of Population
All Patients Entered	Tables for patient allocation and analysis populations, patient disposition
Intent-to-Treat Population	Tables, listings and/or figures for the following: patient disposition, important protocol deviations, patient characteristics, historical diagnoses, pre-existing conditions, previous therapies, concomitant medications, primary and secondary efficacy measures, health outcomes, exploratory measures for the Open-Label Treatment Period (Period 2)
Safety Population	Tables, listings and/or figures for safety assessments, treatment compliance, duration of exposure for the Open-Label Treatment Period (Period 2)

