6.8. Patient Disposition

Patient flow will be summarized from entered to randomized to completion, and analysis populations will be listed and summarized by treatment group.

The following patient disposition summaries will be provided for Open-Label Treatment Period (Period 2):

- The number and percentage of patients in the ITT population completing the Open-Label Treatment Period or prematurely discontinuing from the Open-Label Treatment Period, by treatment group and primary reason for discontinuation. Fisher's exact test will be used to test for treatment differences between treatment groups in the percentage of patients discontinuing from the Open-Label Treatment Period, and in the percentage of patients discontinuing for each reason.
- The number and percentage of patients in the ITT population completing the Open-Label Treatment Period or prematurely discontinuing from the Open-Label Treatment Period, by treatment group, visit, and primary reason for discontinuation.
- The time to discontinuation from the Open-Label Treatment Period due to any reason (in weeks).

Time to discontinuation due to any reason (in weeks) and due to an AE (in weeks) will be summarized graphically for the ITT population by treatment group using Kaplan-Meier techniques. The time to discontinuation (in weeks) from the Open-Label Treatment Period will be calculated as:

$$\frac{(\text{Date of discontinuation from Open-Label Treatment Period} - \text{Date of randomization} + 1)/7}$$

Patients completing the Open-Label Treatment Period will be censored at the date of completion (ie, the date of Visit 11 [Week 52]). Patients without a date of Open-Label Treatment Period completion or discontinuation will be censored at the last nonmissing date out of the following dates: date of last dose and date of last study visit up to and including Visit 11 (Week 52) (scheduled or unscheduled). Descriptive statistics including 25th percentile, median, 75th percentile, and corresponding 95% CIs, as well as probability of discontinuation by Week 52 will be summarized by treatment group. The log-rank test will be used to test for differences in the time to discontinuation between the treatment groups.

The following patient disposition summary will be provided for the Post-Treatment Follow-Up Period (Period 3):

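### The leading TEAE definition closes at the last attended visit, so an event starting or worsening after it, in a patient with neither a Week 52 visit nor an ETV, is neither treatment-emergent nor follow-up-emergent as written

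*SAP*

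**What the plan says.** The leading sentence of SAP 6.15.2.1 counts an event as a TEAE if it begins or worsens "after the first dose of the study medication and on or prior to the date of the last visit within the treatment period". Protocol 10.3.4.1 has the same window: "after the first dose of study treatment and on or prior to the date of the last visit within the treatment period". A follow-up-emergent event (FEAE) is one that "first occurred or worsened in severity after the date of Week 52 (Visit 11) or the ETV". The follow-up tables are restricted further, to patients who "received at least 1 dose of study treatment during Period 2 and have entered the Post-Treatment Follow-Up Period" (SAP 6.1.3).

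Later in the same paragraph, SAP 6.15.2.1 gives a second rule: events with a given lowest level term are "classified as treatment-emergent if they first start on or after the first dose date in the treatment period", or if they are more severe than before treatment. This sentence has no last-visit limit.

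Duration of exposure (SAP 6.15.1) also ends at the "Date of last visit (scheduled or unscheduled) during the treatment period". SAP 6.8 handles the matter differently when it censors time to discontinuation for patients with no completion or discontinuation date. There it takes the last nonmissing of "date of last dose and date of last study visit up to and including Visit 11".

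**The concern.** The two leading definitions are meant to follow on from each other, with the Week 52 visit or ETV as the join. They do so only if every patient has one of those visits. Protocol 8.1.1 and 8.2 expect an ETV after any discontinuation, but a patient who dies cannot attend one, and Protocol 8.3 describes patients who cannot be contacted.

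For such patients the TEAE window closes at the last attended visit and the FEAE window never opens. The event itself can be what prevents the closing visit: a sudden vascular death, an incapacitating stroke or a fatal infection. In Table RHCF.6.7 the listed outputs for MACE, cerebro-cardiovascular events and malignancies, and the main infection table, are built from TEAEs. The AE overview table places TEAEs, treatment-emergent events of special interest, SAEs and deaths side by side. One fatal event between visits could therefore count as an SAE and a death in that table but not as a TEAE.

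**Working it through.** No stated figure needs reproducing for the definitions, so the check sets the rules side by side and then sizes the exposed interval.

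**1. A test case.** The last attended visit is Week 40 (Day 280). A dose is self-injected at Week 44 (Day 308). A fatal infarction occurs at Week 46 (Day 322), with no Week 52 visit and no ETV.

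| Rule | Requirement | Met? |
|---|---|---|
| TEAE, leading sentence | on or before last visit, Day 280 | No: Day 322 is 42 days later |
| FEAE | after Week 52 or ETV | No: neither date exists |
| Follow-up population | entered Period 3 | No |
| TEAE, second sentence | starts on or after first dose date in the treatment period | Yes, if read as having no last-visit limit |
| Doubt rule | start or end date uncertain | Not triggered: date is known |

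The event falls 322 − 308 = 14 days after a dose. The doubt rule closes the list for partial or missing dates in SAP 6.15.2.1, and SAP 6.4.3 ties it to start and end dates and times. It therefore does not rescue a dated event.

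**2. How long the tail can be** (Protocol Section 2, Schedule of Activities).
- Weeks 4 to 16: 28 days between visits.
- Weeks 16 to 40: Days 112, 168, 224, 280, so 56 days each.
- Weeks 40 to 52: 364 − 280 = 84 days, or 84 + 4 + 4 = 92 days with the visit windows.
- Scheduled doses strictly between Weeks 40 and 52 (Table RHCF.2.1): 2 for ixekizumab (Weeks 44 and 48); for adalimumab, 5 (Weeks 42 to 50) or 6 (Weeks 41 to 51).

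**3. How many patients could have such a tail.** Protocol 5.2 assumes 72% completion at Week 52: 550 × 0.72 = 396, which matches its figure. Non-completers: 550 − 396 = 154. The documents do not give the share without an ETV. Assuming 5% to 30%:
- 154 × 0.05 = 7.7, about 8 patients; 154 × 0.30 = 46.2, about 46 patients.
- Assuming also a mean tail of 4 to 6 weeks (half of an 8- to 12-week gap), the uncovered time is 7.7 × 28 / 365.25 = 0.6 to 46.2 × 42 / 365.25 = 5.3 patient-years.

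These are patients with an uncovered interval, not lost events. Most will have no recorded event in it.

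**The case against.** Several points on the other side stand.

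- **Exclusion is not certain.** The second TEAE sentence has no last-visit cut-off, and the TEAE entry in Protocol Appendix 1 speaks only of emergence during a defined treatment period. Against this, the second sentence's own parenthesis explains it as a check against pre-existing conditions, and it states no end date. At best it contradicts the leading sentence.
- **Serious events are kept elsewhere.** The Period 2 SAE and discontinuation tables and the death listing (SAP 6.15.3) are not limited to TEAEs. The registry summary (SAP 6.19) keeps SAEs regardless of TEAE status. Table RHCF.6.7 refers serious infections to the overall SAE table. A reader might infer that these events vanish from the report; the documents do not support that.
- **MACE is ambiguous rather than closed.** A reader might infer that a vascular death between visits can never reach the MACE table. However, Table RHCF.6.7 says that all events qualifying for adjudication will be used for the cerebro-cardiovascular analysis, and it identifies vascular death from an adjudication page without a date window. The TEAE restriction appears in the output column. The program safety analysis plan may supersede these definitions (SAP 6.15.3.1) and is not available here.
- **Little may be recoverable.** AEs are reviewed at visits, so later non-serious events in lost patients are mostly never collected. An event that makes a patient leave is normally followed by an ETV and counted.
- **The rule and the exposure cut-off are the same in both arms.** This does not restore the missing count, because SAP 6.15.2.1 bases AE percentages on numbers of patients, not on person-time.

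**Conclusion.** The gap is real but narrow. It concerns only events that start or worsen after the last attended visit, in patients with neither a Week 52 visit nor an ETV. Under the leading definitions these are left out of TEAE-labelled tables, including the TEAE-based infection and MACE outputs. They are missing from every AE summary table only if they were also non-serious and did not lead to discontinuation. The SAP is inconsistent on the point, since the second TEAE sentence and the adjudication text conflict with the cut-off.

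The number of events affected is unknown and probably small. The range of 8 to 46 patients depends on an assumed 5% to 30% without an ETV and must not be read as a count of lost events. A reader might infer that the ixekizumab versus adalimumab safety comparison is biased in a particular direction. Nothing in the documents shows that; the rule is identical in both arms, and SAP 6.15 treats safety p-values as descriptive.

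The conclusion also assumes that a death or disposition record does not count as a visit, which the documents do not state. If it does count, the gap narrows. It is still worth correcting: MACE counts in 550 patients are likely to be low, so one misclassified event could be visible, and there is no data monitoring committee.

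**What to change.** In SAP 6.15.2.1 and Protocol 10.3.4.1, state one treatment-period end date:

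- For patients with a Week 52 visit or an ETV, keep that visit date.
- Only for patients with neither, use the latest of the last visit, the last dose and the recorded date of discontinuation from Period 2, including discontinuation due to death.
- Classify events starting or worsening after the first dose up to that date as treatment-emergent.

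Reconcile the two TEAE sentences in SAP 6.15.2.1 to this date. In Table RHCF.6.7, do the same for the adjudication and vascular-death text and their TEAE output labels.

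For exposure (SAP 6.15.1), for these patients only, use the later of last visit and last dose. Carrying exposure to the discontinuation or death date would count time long after the last dose as time on drug. Patients who had an ETV should not be drawn into the extended window.

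The cost is a wording change, one extra derived date from data already collected, and slightly longer exposure for a few patients. In those patients the event window may run past the end of exposure. This does not affect the patient-based percentages, but should be noted if exposure-adjusted rates are ever produced.

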6.15.2.2. Common Adverse Events

The number and percentages of patients with common TEAEs will be summarized by treatment group for each treatment period using similar methods described in Section [6.15.2.1](#). Common

TEAEs will be defined as those TEAEs that occurred in $\geq 1\%$ before rounding of total treated patients including all ixekizumab dose regimens. Events will be ordered by decreasing frequency within SOC or PT in the combined ixekizumab dose group.

The following summary tables will be provided for the Open-Label Treatment Period (Safety Population):

- TEAEs, by PT

6.15.3. Deaths, Other Serious Adverse Events, and Other Notable Adverse Events

By-patient listings of deaths, SAEs, and AEs leading to discontinuation will be provided, respectively.

All deaths will be included, regardless of the investigator's or the sponsor's judgment about causality, including the following:

- any deaths occurring during participation in the study in the database for which data are being presented
- any deaths occurring after a patient leaves (is discontinued from or completed) the study in the database for which data are being presented if the death is:
 - the result of a process initiated during the study, regardless of when it actually occurred, or
 - occurs during Period 3 after discontinuation of study drug

An SAE is any AE that results in one of the following outcomes: death; life-threatening, initial, or prolonged hospitalization; disability or permanent damage; congenital anomaly or birth defect; or any other serious/important medical events.

The following summary tables (including treatment group comparison for Period 2) will be provided for the Safety Population during the Open-Label Treatment Period (Period 2):

- SAEs by SOC and PT
- AEs that lead to treatment discontinuation (including death) by SOC and PT

The following summary tables (by treatment group during Period 2) will be provided for the Post-Treatment Follow-Up Population during the Post-Treatment Follow-Up Period (Period 3):

- Follow-up emergent SAEs (FESAEs) by SOC and PT
- FEAEs that lead to treatment discontinuation (including death) by SOC and PT

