- The patient develops a malignancy. **Note**: Patients may be allowed to continue if they develop no more than 2 nonmelanoma skin cancers over any 12-month period during the study.
- The patient develops symptoms suggestive of a lupus-like syndrome and is positive for antibodies against double-stranded DNA.
- If the patient, for any reason, requires treatment with another therapeutic agent that has been demonstrated to be effective for the treatment of PsA or Ps, discontinuation from the study occurs prior to introduction of the new agent.
- Enrollment in any other clinical trial involving an investigational product or enrollment in any other type of medical research judged not to be scientifically or medically compatible with this study.
- The patient develops active suicidal ideation with some intent to act with or without a specific plan (yes to question 4 or 5 on the "Suicidal Ideation" portion of the C-SSRS) or develops suicide-related behaviors as recorded on the C-SSRS. It is recommended that the subject be assessed by a psychiatrist or appropriately trained professional to assist in deciding whether the subject is to be discontinued from the study.
- The patient develops any condition or contraindication as addressed in the local labelling for adalimumab that would preclude the patient from continuing in this protocol.
- The investigator or attending physician decides that the patient should be withdrawn from the study.
- The patient requests to be withdrawn from the study.
- The investigator or Lilly stops the patient's participation in the study or Lilly stops the study for medical, safety, regulatory, or other reasons consistent with applicable laws, regulations, and good clinical practice (GCP).
- The patient becomes HBV DNA positive. The patient should be referred to a specialist physician.
- The patient is diagnosed with an active TB infection.

If in consultation with Lilly or its designee noncompliance is deemed to be significant or if further noncompliance occurs, the patient may be discontinued from the study (see Section 10.3.2.4 Treatment Compliance).

Any patient who permanently discontinues the study treatment for any reason will stop treatment and continue to the ETV prior to entering the Post-Treatment Follow-Up Period (Period 3).

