6.10. Treatment Compliance

Study treatment dispensed will be listed (including the CT Lot number) for all entered patients. Study treatment administration and compliance will be listed for all entered patients.

Patients will record information in a Study Drug Administration Log (captured in the *Exposure* eCRF page), including the date, time, and anatomical location of administration of investigational product, syringe number, who administered the investigational product, and the reason if the investigational product was not fully administered.

Treatment compliance (%) for each patient will be calculated as:

$$100 \times \frac{\text{Total number of injections administered}}{\text{Total number of injections prescribed}}$$

- Number of injections prescribed (that is, expected) is 17 injections for patients on ixekizumab with moderate-to-severe plaque psoriasis. Patients will receive 2 ixekizumab 80 mg injections at Week 0, 1 ixekizumab 80 mg injection every 2 weeks from Week 2 to Week 12, and 1 ixekizumab 80 mg injection every 4 weeks from Week 16 to Week 48.

- Number of injections prescribed (that is, expected) is 14 injections for patients on ixekizumab without moderate-to-severe plaque psoriasis. Patients will receive 2 ixekizumab 80 mg injections at Week 0 and 1 ixekizumab 80 mg injection every 4 weeks from Week 4 to Week 48.
- Number of injections prescribed (that is, expected) is 28 injections for patients on adalimumab with moderate-to-severe plaque psoriasis. Patients will receive 2 adalimumab 40 mg injections at Week 0 and 1 adalimumab 40 mg injection every 2 weeks from Week 1 to Week 51.
- Number of injections prescribed (that is, expected) is 26 injections for patients on adalimumab without moderate-to-severe plaque psoriasis. Patients will receive 1 adalimumab 40 mg injection every 2 weeks from Week 0 to Week 50.
- For patients who discontinue during Period 2, the number of injections prescribed can be derived from the IWRS study drug dispense dataset.
- The total number of injections administered will be derived using the response to the question, “Was dose administered?” on the *Exposure* eCRF page.

Overall compliance for the Open-Label Treatment Period will be considered if the patient misses no more than 20% of the expected doses, does not miss 2 consecutive doses, and does not overdose (that is, take more injections at the same time point than specified in the protocol) within the study period.

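### The SAP's Period 3 table counts follow-up events that end a treatment already stopped, so only deaths can realistically enter it, and the protocol's table of events leading to study discontinuation has no SAP counterpart

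*SAP*

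**What the plan says.** The two documents define the Period 3 discontinuation table differently.

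- **Protocol 10.3.4.1** uses *treatment* discontinuation for its Period 2 summary of adverse events by SOC and PT. For follow-up it changes the term: "AEs that lead to study discontinuation will be summarized by MedDRA system organ class and preferred term for Period 3".
- **SAP 6.15.3** lists, for Period 2, adverse events leading to treatment discontinuation including death. For Period 3 it gives almost the same line with the event type changed: "FEAEs that lead to treatment discontinuation (including death) by SOC and PT".

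A follow-up emergent adverse event (FEAE) is defined in SAP 6.15.2.1 as one that "first occurred or worsened in severity after the date of Week 52 (Visit 11) or the ETV". Protocol 8.1.1 says that a patient who permanently stops study treatment "will stop treatment and continue to the ETV prior to entering the Post-Treatment Follow-Up Period (Period 3").

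SAP 6.15.3 also promises listings: "By-patient listings of deaths, SAEs, and AEs leading to discontinuation will be provided, respectively". Its rules on which deaths to report cover a death that "occurs during Period 3 after discontinuation of study drug".

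**The concern.** A table of events leading to treatment discontinuation makes sense only while there is treatment to discontinue. In Period 3 there is none. The outcome that can still happen is leaving follow-up early, and that is what the protocol asks to see by SOC and PT. It is a real outcome in this design: SAP 6.8 tabulates premature discontinuation from Period 3, and the final database lock waits until every patient has completed or discontinued it.

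The stake is interpretation. If the SAP line is programmed as written, the report will contain a table whose title suggests that discontinuing events were looked for, with no non-fatal rows. A reader could take that as reassurance about safety after treatment, when the table could hardly have shown anything else.

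**Working it through.** No sample size, power or error rate is involved. The check is which events could satisfy the SAP criterion, and whether another SAP output covers the protocol's summary.

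**1. When a follow-up emergent event can start.** After the Week 52 visit or the Early Termination Visit (SAP 6.15.2.1).

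**2. When treatment ends, early discontinuers.** Treatment stops before the Early Termination Visit, which itself precedes Period 3 (protocol 8.1.1). Any follow-up emergent event therefore comes after treatment has stopped.

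**3. When treatment ends, completers.** SAP 6.10 gives the last scheduled injections as Week 48 for ixekizumab, Week 50 for adalimumab without moderate-to-severe psoriasis, and for adalimumab with it "1 adalimumab 40 mg injection every 2 weeks from Week 1 to Week 51". The latest is Week 51, and 51 × 7 = day 357. The protocol's Schedule of Activities sets the Week 52 visit at day 364 ± 4, so no earlier than 364 − 4 = day 360. Even the latest scheduled dose falls 360 − 357 = 3 days before the earliest in-window Week 52 visit.

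**4. Events carried over from Period 2.** An event that caused withdrawal in Period 2 and worsened later might seem to qualify. SAP 6.15.2.1 says of a follow-up event already counted as treatment-emergent that "it will not be counted as a follow-up emergent event".

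**5. Deaths.** The SAP line includes death, so fatal follow-up events can appear.

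From steps 1 to 5, the fatal part of the table can be filled and the non-fatal part has essentially no possible entries.

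**6. Whether another SAP output gives the protocol's summary.**

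| SAP output | Covers Period 3? | Identifies events leading to exit? | By SOC and PT? |
|---|---|---|---|
| Adverse event overview (6.15.2.1) | No, Period 2 only | Yes | No |
| FEAEs by maximum severity (6.15.2.1) | Yes | No | Yes |
| Follow-up emergent serious events (6.15.3) | Yes | No | Yes |
| Period 3 disposition by primary reason (6.8) | Yes | By reason only | No |
| By-patient listing of events leading to discontinuation (6.15.3) | Not restricted by period | Yes, but treatment or study not stated | Not a summary table |

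None of these gives, by treatment group, SOC and PT, the events after which patients left follow-up.

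**The case against.** Four points can be made for the SAP.

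*Little is lost.* Every follow-up emergent event is tabulated by severity, serious ones have their own table, departures are summarised by reason, and the listing is not limited to Period 2. This stands. A reader might infer that the table is empty or that events disappear from the report. The documents support neither: the line includes deaths, and the events remain visible in the other outputs.

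*The exclusion in step 4 may be narrower than it looks.* The sentence sits among rules for missing or doubtful dates. Applied to everything, it fits awkwardly with a definition that admits worsening after the Early Termination Visit. On the narrow reading, an event that stopped treatment in Period 2, was ongoing at that visit and then worsened could enter the table. This is why the conclusion is *essentially no* non-fatal entries, not *none*. Such an entry would still describe a withdrawal from drug in Period 2, not a departure from follow-up, so it would not supply the protocol's summary.

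*The wording is loose throughout.* For Period 2 the protocol overview counts discontinuation from treatment, while the SAP overview counts discontinuation from the study. A reader might infer that the sponsor chose to drop an analysis. The documents do not show that. The SAP revision history records changes to 6.15.3.1 but none to 6.15.3, and the line closely matches its Period 2 counterpart, which looks more like carried-over text.

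*The protocol leaves analysis details to the SAP.* Section 10.3.1 does so, and requires a documented justification only for changes affecting the primary and major secondary endpoints. That limits the seriousness of the departure. It does not make the table informative.

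**Conclusion.** The point holds in a limited form. SAP 6.15.3 applies a treatment-period criterion to an off-treatment period, and the protocol's Period 3 summary of events leading to study discontinuation has no equivalent SAP table.

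The effect is confined to one descriptive safety table. Table RHCF.6.1 plans no treatment comparison in Period 3, and no efficacy endpoint, error rate or Period 2 safety comparison is affected. The number of non-fatal events that would go unsummarised is unknown, because the documents give no rate of event-related departure from follow-up.

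The conclusion assumes that *treatment* in the SAP line means study drug, that no dose is taken after the Week 52 or Early Termination Visit, and that events already counted as treatment-emergent are not counted again. If the last assumption fails, a few carried-over events could appear, with the limited meaning described above. This is a minor point, but the line is wrong as written.

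**What to change.** In SAP 6.15.3, redefine the second Period 3 table as follow-up emergent adverse events leading to discontinuation from the study during the Post-Treatment Follow-Up Period, deaths included, by SOC and PT.

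Exchanging *treatment* for *study* alone would leave the term ambiguous. Protocol 8.2 and 9.4.5.4 also describe a patient as discontinuing the study when that patient leaves Period 2 and then enters follow-up. Naming the follow-up period removes the doubt and delivers what protocol 10.3.4.1 plans.

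The cost is one phrase in the SAP and the matching table specification. No design feature, endpoint or hypothesis test changes.
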